11.2.2. Outpatient Assessments: Days 1-14

The following subject assessments and procedures will be conducted by the subjects at home/away from the clinic in the morning, at midday, and in the evening. For Days 1, 4 and 14, these assessments are in addition to the clinic visit assessments. Throughout the study, site staff

will be instructed to review the ePRO/eDiary administration portal to ensure subject compliance with completion of the following ePRO assessments, study drug dosing, and use of rescue medications.

Morning: Subjects should take the first daily dose of study drug (am dose; 6-8 am) with approximately 4-6 ounces of water, and then perform the following assessments between 8-10 am:

- Subject rating of pain (NRS) for the average level of pain over the last 12 hours
- Subject rating of pain (NRS) for the average level of pain over the past 1 hour
- Quality of sleep

Midday: Subjects should take the second daily dose of study drug (midday dose; 12-2 pm) with approximately 4-6 ounces of water.

Evening: Subjects should take the third daily dose of study drug (evening dose; 6-8 pm) with approximately 4-6 ounces of water, and perform the following assessments between 8-10 pm:

- Subject rating of pain (NRS) for the average level of pain over the last 12 hours
- Subject rating of pain (NRS) average pain over the past 1 hour
- Rating of pain using NRS, for average pain at rest or movement
- Daily activities (sedentary, walking activities, etc.) to be recorded by the subject at the end of the day
- Use of any rescue medications throughout the day

11.2.3. Clinic Visit 2: Day 4 (± 1 Day)

On Day 4, subjects return to the clinic to undergo the following assessments:

- Alcohol breathalyzer and urine drug screen. A positive test result for urine drug or alcohol breathalyzer at any time during the study will terminate the subject from further participation in the study.
- Abbreviated physical examination
- Neurological examination
- Vital signs
- Document AEs
- Subject rating of pain (NRS) “right now” via the site study-provisioned tablet
- Subject rating of medication helpfulness via the site study-provisioned tablet
- Global clinical impression of improvement by the physician (CGI-C) via the site study provisioned tablet

- Global impression of improvement by the subject (PGI-C) via the site study-provisioned tablet
- Functionality assessment:
 - Fingers to Floor Distance (FFD)
- VAS via the site study-provisioned tablet
- Disability assessment at Day 4:
 - Oswestry Disability Index (ODI) via the site study provisioned tablet
- For the select group of sites and subjects who will undergo PK assessments, a single blood sample will be drawn on Day 4 after all other assessments have been completed.
- Any changes or additions to prior concurrent medication use will be recorded. Confirm that no rescue medications were taken on Day 4 (Visit 2).
- Site staff to review returned study drug and rescue medication against the eDiary dosing information to evaluate compliance.

11.2.4. Clinic Visit 3: Day 14 (+ 1 Day, End of Treatment/Early Termination)

On Day 14, subjects return to the clinic to undergo the following assessments:

- Abbreviated physical examination
- Neurological examination
- Vital signs
- Document AEs
- Subject rating of pain (NRS) “right now” via the site study-provisioned tablet
- Subject rating of medication helpfulness via the site study-provisioned tablet
- Global clinical impression of improvement by the physician (CGI-C) via the site study-provisioned tablet
- Global impression of improvement by the subject (PGI-C) via the site study-provisioned tablet
- Functionality assessment:
 - Fingers to Floor Distance (FFD)
- Alcohol breathalyzer and urine drug screen
- Disability assessment:
 - Oswestry Disability Index (ODI) via the site study-provisioned tablet
- Urine pregnancy test for all females of childbearing potential
- Laboratory evaluations

- 12-Lead ECG
- Any changes or additions to prior concurrent medication use will be recorded. Confirm that no rescue medications were taken on Day 14 (Visit 3).
- Site staff to review returned study drug and rescue medication against the eDiary dosing information to evaluate compliance.
- Site staff to collect smartphone, if provisioned

In the event that a subject discontinues or is withdrawn from the study early, the Day 14/EOT assessments should be completed at an Early Termination visit.

11.2.5. Clinic Visit 4: Day 28 (+3 Days, Follow-Up Visit)

Prior to discharge from the clinical study, the following procedures should be performed:

- AEs will be recorded.
- Any changes or additions to prior concurrent medication use will be recorded.
- Vital signs
- Abbreviated physical examination
- Urine pregnancy test for all females of childbearing potential

12. STUDY PROCEDURES

12.1. Numerical Rating Scale to Assess Subject's Pain Level due to Muscle Spasm

The NRS is a scale of 0 to 10 (0=no pain, 10=worst possible pain). Subjects will use the NRS to evaluate their pain ("right now") on Day 1 (baseline assessment) and on Days 4 (Visit 2) and 14 (Visit 3) during the clinic visit via the site study-provisioned tablet.

In addition, the NRS scale will be used by subjects for pain assessment at rest and upon movement in the evening (8–10 pm) on Days 1 to 14 recorded via the subject smartphone/use of trial application. Subjects will also be asked to rate their average pain level (NRS scale) over the past hour and the past 12 hours in the morning (8-10 am) and evening (8-10 pm) via the subject smartphone/use of trial application.

12.2. Subject Rated Medication Helpfulness (SRMH)

The SRMH is a categorical scale for subjects to assess medication helpfulness, where 1=poor, 2=fair, 3=good, 4=very good, and 5=excellent. Medication helpfulness will be administered via the site study-provisioned tablet ePRO during the clinic visit on Days 4 and 14.

12.3. Clinical Global Assessments (Clinician's Global Impression of Severity, CGI-S and Clinician's Global Impression of Change, CGI-C)

On Day 1, the CGI-S will be conducted by the physician using a 1-5 scale (1=no pain, 2=mild pain, 3=moderate pain, 4=severe pain, and 5=worst possible pain).

The CGI-C will be conducted by the physician on Days 4 (Visit 2) and 14 (Visit 3) to assess global improvement using a 7-point scale (1=Very Much Worse, 2=Much Worse, 3=Minimally Worse, 4=No Change, 5=Minimally Improved, 6=Much Improved, and 7=Very Much Improved).

The Investigator/evaluator will be provided with training to ensure consistent CGI-S and CGI-C assessments across investigational centers. To the greatest extent possible, the assessments for a particular subject should be performed by the same rater/evaluator at all study visits.

12.4. Subject-Rated Global Assessments (Patient's Global Impression of Severity, PGI-S and Patient's Global Impression of Change, PGI-C)

On Day 1 (Screening/Baseline visit), the PGI-S will be administered to assess the subject's impression of severity of pain using a 1-5 scale (1=no pain, 2=mild pain, 3= moderate pain, 4=severe pain, and 5=worst possible pain).

The PGI-C will be administered on Days 4 (Visit 2) and 14 (Visit 3) to assess the subject's global impression of improvement using a 7-point scale (1=Very Much Worse, 2=Much Worse, 3=Minimally Worse, 4=No Change, 5=Minimally Improved, 6=Much Improved, and 7=Very Much Improved).

12.5. Visual Analogue Scale (VAS)

The VAS for subject-reported sleepiness will be measured in the clinic on Day 4 (Visit 2) using a visual analog scale from 0 = alert, wide awake; to 10 = very sleepy, difficulty remaining awake.

12.6. Functionality Assessment

On Day 1 (Screening/Baseline visit) and on Days 4 (Visit 2) and 14 (Visit 3), the subject's functionality based on the Fingers to Floor Distance (FFD) test will be assessed at the clinical site. FFD is measured as the distance in cm from the patients right long finger to the floor when standing with the spinal cord flexed with complete extension of knee joint. The FFD should be conducted at the same time of day for each test on Days 1, 4, and 14. The Investigator/evaluator will be provided with training to ensure consistent FFD assessments across investigational centers. To the greatest extent possible, the assessments for a particular subject should be performed by the same evaluator at all study visits.

12.7. Oswestry Disability Index (ODI)

Disability will be assessed by the subject using the Oswestry Disability Index, which is based on 10 questions with one answer each for: pain intensity, personal care, lifting, walking, sitting, standing, sleeping, sex life [if applicable], social life, and traveling). This will be conducted on

Day 1 (Screening/Baseline visit) and on Days 4 (Visit 2) and 14 (Visit 3) via the site study-provisioned tablet .

12.8. Use of Rescue Medications

Concomitant use of rescue analgesia used during the study will be recorded as concomitant medications on the eCRF (see [Section 14](#) for allowed and disallowed medications during the study) and will be analyzed at the time of report following dosing of study drug through Visit 4 (Day 28). Subjects will receive acetaminophen (500 mg tablets) (Tylenol) for use as rescue medication if needed for pain during the study. Use of rescue medication will be recorded daily via smartphone/use of trial application . Subjects are instructed to not take any rescue medications on the day of the clinic visits, Days 4 (Visit 2) and 14 (Visit 3).

12.9. Vital Signs

Vital signs will include the measurement of supine and standing blood pressure, orthostatic assessments, sitting heart rate (after approximately 3 minutes at rest), respiratory rate, and body temperature. Vital signs will be measured on Day 1 (Screening/Baseline visit) and on Days 4, 14, and 28 (All Visits). Weight and height will be measured at Screening/Baseline only.

12.10. 12-Lead Electrocardiograms

Standard 12-lead ECGs will be administered at the clinic on Day 1 (Screening/Baseline visit) and on Day 14 (Visit 3). Normal, abnormal (not clinically significant or clinically significant) are collected.

12.11. Clinical Laboratory Assessments

A certified laboratory will be used as a central laboratory to perform all routine hematology, clinical chemistry, and urinalysis assessments. Planned laboratory analyses include:

Category	Test Name
Hematology	Hemoglobin Hematocrit Platelets Prothrombin Time (PT) ^a Red blood cells White blood cells with differential (absolute)
Chemistry	Alanine aminotransferase (ALT) Aspartate aminotransferase (AST) Alkaline phosphatase Blood urea nitrogen (BUN) Creatinine Gamma glutamyltransferase (GGT) Glucose Potassium Sodium Total and direct bilirubin Thyroid stimulating hormone (TSH) ^a
Urinalysis	Bilirubin Occult blood Glucose Ketones Leukocytes Nitrite pH Protein Specific gravity Urobilinogen
Other	Urine drug and alcohol breathalyzer ^{b,c} Urine pregnancy ^d

Note: The complete panel of safety labs (other than where footnoted) will be completed on Day 1 (Screening/Baseline visit) and Day 14.
 
^a Screening only.
 
^b Day 1 (Screening/Baseline), Day 4, and Day 14 (End of Treatment).
 
^c Includes testing for amphetamines, methamphetamines, barbiturates, benzodiazepines, cannabinoids, cocaine, opiates – ethanol will be determined by breathalyzer.
 
^d Urine pregnancy test at Days 1, 14, and 28 for females of childbearing potential.
	

12.12. Blood Collection for Tolperisone Plasma (PK) Concentrations (Optional)

In a subset of subjects (approximately 120) at select sites, blood samples for the determination of plasma tolperisone concentrations will be drawn on Day 4 (Visit 2) after completion of all study assessments. The results from the analyses will be used for determination of population PK of tolperisone.

Plasma samples will be analyzed for tolperisone using a validated liquid chromatography with tandem mass spectrometric detection (LC/MS/MS) method (limit of quantification [LOQ]: 1 ng/mL).

Results will not be included in the Clinical Study Report.

12.12.1. Sample Storage and Shipment

The samples will be frozen as soon as possible (within 4 hours) of collection and stored frozen at -20°C until time of shipment to the central laboratory (ACM). All samples will be shipped frozen with sufficient dry ice to maintain frozen conditions for at least 72 hours at times arranged between the study site and the laboratory. Please refer to the ACM Laboratory Manual for detailed instructions.

12.13. DNA Genotype

A blood sample will be collected at baseline for DNA genotype screening for CYP450 2D6 polymorphism. No other DNA testing will be performed. Samples will be shipped to the genotyping laboratory (Machaon) and stored until ready for use by the Sponsor. Samples will be labeled with a unique sample identification label and will not include any protected subject health information. Any results from future testing will not be provided to the site or subjects. Samples will be stored in a secure, limited access facility indefinitely, or disposed. Samples will be inventoried and traceability will be maintained as to where samples are stored and how samples are used (assay validation, or research and development). Please refer to the Machaon Laboratory Manual for detailed instructions.

12.14. Blood Collection Volume for the Study

Up to 48 mL of blood will be collected for screening and EOT/ET clinical laboratory evaluations. In addition, a blood sample (approximately 5 mL) will be collected at baseline for DNA genotype screening for CYP450 2D6 polymorphism. In a subset of subjects (N=80), approximately 5 mL (1 x 5 mL samples) will be collected for PK analysis.

12.15. Medical History

A medical history will be performed at Screening/Baseline (Day 1). Each subject's history of alcohol and drug use will be evaluated. Continued eligibility and adherence to protocol restrictions will be confirmed throughout the study.

12.16. Physical and Neurological Examination

A physical and neurological examination will be performed at Screening/Baseline (Day 1), on Day 4, and on Day 14. Only a physical examination will be performed on Day 28 (Visit 4). A physical examination will be performed at Screening/Baseline (Day 1). All other physical examinations may be abbreviated (i.e. disease-specific and symptom directed).

12.17. Pregnancy Test

A urine pregnancy test will be performed at Screening/Baseline for all females of childbearing potential. A urine pregnancy test will also be collected at Days 14 (Visit 3) and 28 (Visit 4) for females of childbearing potential. A positive pregnancy test at any time during the study will immediately terminate the subject from further participation in the study.

13. STUDY DRUG

The Sponsor will supply tolperisone 50, 100, 150, and 200 mg tablets and matching placebo in a blinded fashion. Each subject will be provided with one bottle of study drug containing 42 tablets for 14 days of TID dosing. The study drug will be self-administered (TID) by the subjects. Each subject will also be provided with one bottle of rescue medication (acetaminophen 500 mg) containing 50 caplets (as is standard commercial packaging).

Study drug and rescue medication should be stored at controlled room temperature (15-30 °C [59-86 °F]) and locked in a secure cabinet or room.

13.1. Study Drug Administration

Tolperisone 50, 100, 150, and 200 mg, or matching placebo should be taken by the subjects TID, at 6-8 am, 12-2 pm, and 6-8 pm on Days 2 to 14; the first dose of study drug will be administered by the subject on Day 1.

All study medications will be administered orally with approximately 4-6 ounces of water. The subjects will be instructed to swallow the study tablet whole, without chewing the tablet. The subjects may take the study drug with or without food.

Subjects will be prompted via reminders on their smartphone/trial application to take their study drug at least 1 hour before and within 2 hours of the morning and evening assessments.

- Subjects in Group A (n=80) will be randomized to receive (1) 50 mg tolperisone tablet, TID for 14 days, for a total daily dose of 150 mg.
- Subjects in Group B (n=80) will be randomized to receive (1) 100 mg tolperisone tablet administered TID for 14 days, for a total daily dose of 300 mg.
- Subjects in Group C (n=80) will be randomized to receive (1) 150 mg tolperisone tablet administered TID for 14 days, for a total daily dose of 450 mg.
- Subjects in Group D (n=80) will be randomized to receive (1) 200 mg tolperisone tablet administered TID for 14 days, for a total daily dose of 600 mg.
- Subjects in Group E (n=80) will be randomized to receive (1) placebo tablet administered TID for 14 days.

13.2. Accountability

The Investigator or designated study personnel is responsible for keeping accurate records of the clinical supplies received from the Sponsor and the study drug administered to each subject. The study monitor(s) will review study drug records periodically during the conduct of the study. At the end of the study, all partial and empty containers must be returned to the Sponsor or they must be destroyed at the clinical study site according to site standard operating procedures (SOPs). Records of destruction of study drug at the study site must include bottle identifying information and number of tablets in each bottle.

14. SUBJECT RESTRICTIONS

Subjects are to abstain from using psychoactive prescription or non-prescription medications, psychoactive nutritional supplements or herbal preparations during their participation in the study.

Subjects are to abstain from using any medication or dietary supplement to promote sleep, including over the counter sleep medications, during their participation in the study.

Subject will abstain from using antihistamine or any other drugs that can cause drowsiness, and will discuss any new prescription with the Investigator.

Other medications that the subject routinely takes will be discussed and reviewed by the PI. All concomitant medication taken during the trial should be recorded with indication, daily dose, and start and stop dates of administration.

Subjects will receive study-provided rescue medication of acetaminophen tablets (500 mg) that can be taken up to 3 times per day as rescue medications if their pain is severe. All rescue medication should be entered via the smartphone/use of trial application daily through Day 14 (Visit 3). Rescue medication is not to be taken on Days 4 (Visit 2) or 14 (Visit 3).

14.1. Fluid, Food, and Lifestyle Restrictions

Subjects are not allowed to consume alcoholic beverages prior to their study visit on Days 1, 4, and 14. At all other times, alcohol consumption is limited to no more than 2 alcoholic drinks or equivalent (beer [24 ounces or 710 mLs], wine [12 ounces or 355 mLs], or distilled spirits [3 ounces or 89 mLs]) per day.

Caffeinated beverages will be permitted to no more than 4 units per day amounts (1 unit = 120 mg caffeine or about one eight-ounce cup of coffee).

Subjects are to refrain from vigorous physical activity, heat and ice packs and non-pharmacological therapies (e.g. acupuncture, chiropractic adjustment, massage, TENS, physiotherapy, etc.) during Days 1 to 14.

15. DISCONTINUATION CRITERIA AND PROCEDURES

According to the Declaration of Helsinki, all subjects have the right to withdraw from a study at any time, regardless of their reasons. In addition, it is the right of the Investigator to remove subjects from the study as a result of AEs, protocol violation, or any other reason.

15.1. Premature Termination of Study/Closure of Study Sites

The study may be terminated prematurely if results affecting the safety of the subjects become available. A site may be closed prematurely if recruitment is too slow, poor quality data is produced, or there is evidence of attempted or proven fraud.

In the event the Sponsor prematurely terminates the study, the Investigator will promptly notify the IRB.

16. EVALUATION AND REPORTING OF ADVERSE EVENTS

16.1. Adverse Event (AE) Definitions

An AE is defined as any untoward medical occurrence in a subject administered a medicinal product and which does not necessarily have to have a causal relationship with this treatment. AEs occurring after the initiation of the treatment are referred to as treatment-emergent adverse events (TEAEs). An AE can therefore be any unfavorable and unintended sign (for example, an abnormal laboratory finding), symptom, or disease temporally associated with the use of a medicinal product, whether or not considered related to this medicinal product.

A suspected adverse reaction is any AE for which there is a reasonable possibility that the drug caused the AE. ‘Reasonable possibility’ means there is evidence to suggest a causal relationship between the drug and the AE. A suspected adverse reaction implies a lesser degree of certainty about causality than adverse reaction, which means any AE caused by a drug.

An AE may be:

- A new illness,
- Worsening of a concomitant illness,
- An effect of the study medication including comparator; it could be an abnormal laboratory value as well as a significant shift from baseline within normal range which the Principal Investigator or medically qualified designate considers to be clinically important.

Surgical procedures themselves are not AEs. They are therapeutic measures for conditions that require surgery. The condition for which the surgery is required is an AE, if it occurs or is detected during the study period. Planned surgical measures permitted by the clinical study protocol and the condition(s) leading to these measures are not AEs, if the condition(s) was (were) known before the start of study treatment. In the latter case, the condition should be reported as medical history.

An SAE or reaction is any untoward medical occurrence that at any dose:

- Results in death,
- Is life-threatening,
- Requires inpatient hospitalization or prolongation of existing hospitalization,
- Results in persistent or significant disability or incapacity (defined as a substantial disruption of a person’s ability to conduct normal life functions),
- Is a congenital anomaly or birth defect,
- Is an important medical event (including development of drug dependence or drug abuse) that may jeopardize the subject or may require intervention to prevent one of the other outcomes listed above (according to medical judgment of the Principal Investigator).

16.1.1. Severity Assessment

All AEs will be graded as mild, moderate, or severe according to the following definitions:

Mild: Causing no limitation of usual activities; the subject may experience slight discomfort.

Moderate: Causing some limitation of usual activities; the subject may experience annoying discomfort.

Severe: Causing inability to carry out usual activities; the subject may experience intolerable discomfort or pain.

Every effort will be made to obtain an adequate evaluation of the severity.

16.1.2. Causality Assessment

Investigators are required to assess the causal relationship (i.e., whether there is reasonable possibility that the study drug caused the event) using the following definitions:

- **Unrelated**: another cause of the adverse event is more plausible; a temporal sequence cannot be established with the onset of the adverse event and administration of the study agent; or a causal relationship is considered biologically implausible.
- **Possibly Related**: There is a clinically plausible time sequence between onset of the adverse event and administration of the study agent, but the adverse event could also be attributed to concurrent or underlying disease, or the use of other drugs or procedures. Possible related should be used when the study agent is one or several biologically plausible adverse event causes.
- **Definitely Related**: The adverse event is clearly related to use of the study agent.

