16.3. Serious Adverse Event Reporting

The sites will notify the sponsor and sponsor's designee of any SAE, without regard to causality, within 24 hours after becoming aware of its occurrence.

If, during follow-up, any non-serious AE worsens and eventually meets the criteria for an SAE, that AE should be recorded as a new SAE.

The initial SAE report must be as complete as possible, including details of the current illness and SAE, and an assessment of the causal relationship between the event and the investigational product(s). Information not available at the time of the initial report (e.g., an end date for the AE, laboratory values received after the report, or hospital discharge summary) must be documented. All follow-up information must be reported as soon as the relevant information is available.

The SAE notification should be reported by completing the SAE report form in the EDC.

An SAE will be considered "unexpected" if the AE is not listed in the Investigator's Brochure or is not listed at the specificity or severity that has been observed; or, if an Investigator's Brochure is not required or available, is not consistent with the risk information described in the General Investigational Plan or elsewhere in the current application. "Unexpected," as used in this definition, also refers to AEs that are mentioned in the Investigator's Brochure as occurring with a class of drugs or as anticipated from the pharmacological properties of the drug, but are not specifically mentioned as occurring with the particular drug under investigation.

The sites will determine whether any serious unexpected related AE must be reported to the IRB. If so, the event will be reported via fax or email or as required per IRB once the Investigator or staff becomes aware of the event.

The sponsor will determine whether the SAE must be reported in an expedited manner to the appropriate regulatory agencies. If so, the Sponsor will report the event to the appropriate regulatory agencies, and all participating Investigators.

If reports of any new and unexpected AEs become available to the Sponsor during the clinical portion of this study (related or not to the present study), the Sponsor must advise the sites of those events.

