- Overall summary of number of unique TEAEs and treatment-emergent serious adverse events (SAEs) and subject incidence of TEAEs meeting various criteria;
- Subject incidence of TEAEs by MedDRA system organ class and preferred term;
- Subject incidence of TEAEs by MedDRA preferred term;
- Subject incidence of TEAEs by severity grade, MedDRA system organ class, and preferred term;
- Subject incidence of TEAEs by relationship to study drug, MedDRA system organ class, and preferred term;
- Subject incidence of SAEs by MedDRA system organ class and preferred term;
- Subject incidence of TEAEs Leading to Study Drug Discontinuation by MedDRA system organ class and preferred term; and
- Subject incidence of TEAEs by CYP450 2D6 Genotype, MedDRA system organ class and preferred term.

- Subject incidence of After-treatment Adverse Events by MedDRA preferred term.

At each level of summarization (e.g., any AE, system organ class, and preferred term), subjects experiencing more than one AE will be counted only once. In the summary of TEAEs by severity grade, subjects will be counted once at the highest severity reported at each level of summarization; in the summary of TEAEs by relationship, subjects will be counted once at the closest relationship to study drug. Related events include those reported as “Possibly Related” or “Definitely Related” to study drug; events considered not related are those reported as “Unrelated” to study drug.

Adverse event data will be presented in data listings by patient, treatment group, and event. The study phase (e.g., treatment-emergent, after-treatment) will also be presented in the listing. Serious AEs and AEs leading to discontinuation, interruption or dose reduction, interruption of the study drug will be presented in separate data listings.

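### The causality categories in Protocol 16.1.2 overlap: an event with a plausible drug cause and a likelier alternative can be coded either Unrelated or Possibly Related

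*Protocol*

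**What the plan says.** Protocol 16.1.2 asks investigators to judge whether there is a reasonable possibility that study drug caused the event, and then gives three categories.

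- **Unrelated** has three criteria. The first is that "another cause of the adverse event is more plausible". The second is that no temporal sequence can be established. The third is introduced by "or a causal relationship is considered biologically implausible". The list is joined by 'or', so any one criterion suffices.
- **Possibly Related** needs two things: "There is a clinically plausible time sequence between onset of the adverse event and administration of the study agent", and that "the adverse event could also be attributed to concurrent or underlying disease, or the use of other drugs or procedures". A usage instruction follows: "Possible related should be used when the study agent is one or several biologically plausible adverse event causes".
- **Definitely Related** is kept for events clearly related to study drug.

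Protocol 16.1 sets the general standard: "A suspected adverse reaction is any AE for which there is a reasonable possibility that the drug caused the AE". It explains reasonable possibility as evidence suggesting a causal relationship.

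SAP 7.5.2 reduces the three categories to two. Possibly and Definitely Related count as related, and "events considered not related are those reported as" Unrelated. Each subject is counted once, at the closest relationship. Neither document gives a rule for recoding or adjudicating the site's assessment.

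Relatedness also drives two actions. Protocol 16.2 asks for every effort to establish the final outcome of related events, and Protocol 16.3 states: "The sites will determine whether any serious unexpected related AE must be reported to the IRB".

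**The concern.** The first Unrelated criterion is comparative: it asks whether something else is the likelier cause. Possibly Related and the general standard in 16.1 are not comparative: they ask whether the drug is a credible cause at all. An event can pass the second test and fail the first. Two investigators could then code the same event differently, and both would comply with the protocol.

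Such events are foreseeable here. Subjects have acute back pain, stop their previous analgesics and muscle relaxants at entry, and may take acetaminophen as rescue, so other explanations for a symptom will often be available. About 45 sites make the judgement. Safety and tolerability is a secondary objective of a study meant to identify the Phase 3 dose. Its relationship table should therefore not depend on which line of a definition a site happens to apply, nor leave out events that the protocol itself would call suspected adverse reactions.

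**Working it through.** The plan states no figure for related events, so there is nothing to reproduce. The check is one of logic.

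**Test case:** an event with plausible timing, a biologically plausible drug cause, and another cause judged more plausible.

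| Provision | Requirement | Met? |
|---|---|---|
| Unrelated, criterion 1 (Protocol 16.1.2) | Another cause more plausible | Yes, and sufficient alone |
| Unrelated, criterion 2 | No temporal sequence | No, but not needed |
| Unrelated, criterion 3 | Biologically implausible | No, but not needed |
| Possibly Related, timing | Plausible sequence | Yes |
| Possibly Related, other attribution | Could also have another cause | Yes; no ceiling on how likely that cause is |
| Possibly Related, usage instruction | Drug among the plausible causes | Yes; it need not be the likeliest |
| Suspected reaction (Protocol 16.1) | Reasonable possibility, i.e. evidence suggesting causation | Yes, where such evidence exists |

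1. The case satisfies both Unrelated and Possibly Related, so the categories are not mutually exclusive.
2. No sentence in 16.1.2 or elsewhere in the two documents says which category prevails.
3. The case can meet the 16.1 definition of a suspected adverse reaction and still be coded Unrelated in compliance with 16.1.2.
4. The SAP draws its line exactly between these two categories, so the ambiguity passes straight into the analysis.

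**Illustration only.** Inputs: 80 subjects per arm (Protocol 13.1) and headache incidence of 14.2% in healthy-volunteer studies and 15.3% in patient studies (Protocol 7.1). The share of headaches with a likelier other cause is not in the documents; 25% to 75% is assumed. It is also assumed that all other headaches are coded related and that all sites apply the same line.

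- Headaches per arm: 80 × 0.142 = 11.4; 80 × 0.153 = 12.2.
- Events per arm whose code depends on the line applied: 11.4 × 0.25 = 2.8 up to 12.2 × 0.75 = 9.2.
- Related rate at 14.2% incidence under the Possibly Related line: 14.2%.
- Related rate under the Unrelated line: 14.2% × (1 − 0.25) = 10.7% with a 25% share; 14.2% × (1 − 0.75) = 3.6% with a 75% share.

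If sites differ in the line they apply, the result falls between these values and 14.2%.

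**The case against.** The strongest reply is that the lead-in to 16.1.2 already states the governing test, and that Possibly Related carries the section's only instruction on when a category should be used. Read together, these would send an event with a genuine plausible drug cause to Possibly Related. That is a sensible reading, and it is the one the fix would write down. But the Unrelated line is just as explicit and nothing subordinates it, so a site that applies it as printed is not in error.

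The limits on the consequences do stand:

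- SAEs are notified within 24 hours regardless of causality, and the sponsor decides on expedited regulatory reporting (Protocol 16.3).
- The investigator attempts to resolve, or determine the status of, any event unresolved at the last visit, related or not (Protocol 16.2).
- TEAEs and SAEs are tabulated regardless of relationship (Protocol 17.4.3.1, SAP 7.5.2), and those tables carry the comparison with placebo.
- Assessment is double-blind and randomization is stratified by site (SAP 6.3.2). Differences in coding between sites should therefore fall roughly equally on the arms.

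A reader might also infer a gap: that an event with plausible timing and no alternative cause, yet not clearly related, fits no category. The text does not support this. The usage instruction as printed reads "Possible related should be used when the study agent is one or several biologically plausible adverse event causes". Its wording can include the drug as the sole plausible cause, even though the preceding sentence presupposes an alternative.

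A reader might likewise take a contrast such as 3.6% against 14.2% as the expected effect. That is only the extreme end of an assumed range. The headache rates come from other studies, including one in multiple sclerosis at up to 900 mg/day for up to 48 weeks (Protocol 7.1 and 7.3.2), so they are weak guides to 14 days of treatment for acute back spasm.

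**Conclusion.** The overlap is real and follows from the printed definitions alone, without any numerical assumption. The first Unrelated criterion also conflicts with the reasonable-possibility standard that the protocol sets in 16.1 and repeats at the head of 16.1.2.

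The effect is confined to outputs and actions that depend on relatedness: the TEAE-by-relationship table, the added effort on final outcome for related events, and site decisions on IRB reporting of serious unexpected related events. It does not reach total TEAE or SAE counts, 24-hour SAE notification or efficacy. A reader might infer that the safety comparison between doses and placebo is biased. The documents do not support that, because blinding and site-stratified randomization make the miscoding roughly non-differential. It mainly shifts the level of the related-event rates and dilutes contrasts between arms in that one table.

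The size cannot be estimated from the documents, because they do not give the share of events with a likelier other cause. This merits correction as a definitional fault; it does not threaten the trial's main conclusions.

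**What to change.** In Protocol 16.1.2:

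1. Replace the first Unrelated criterion with: *there is no reasonable possibility that study drug caused the event*.
2. Add that an event for which study drug is a plausible cause is at least Possibly Related, even if another cause is more plausible.

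Carry the same wording into any site instructions for completing the eCRF. Those instructions are not among the documents, so whether they already deal with the point is unknown.

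Apply the change prospectively. If events have already been coded, have them re-assessed blind before unblinding, so that one table does not mix two standards. This may well be needed: SAP 7.7.2 reports a May 2019 audit of misconduct at one site during the trial, which shows that the trial was already under way when the SAP was written.

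The cost is wording in one section and its guidance, with no new data collection, plus some re-assessment work if the change comes late. Related-event rates will be somewhat higher, as the protocol's own definition of a suspected reaction implies.
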